F.7.iii: *Maintenance and Sustainability (32 months)*: Maintenance: After the goals of >80% screening rate with > 80% protocol fidelity is achieved for 6 months, implementation will be considered successful. The Control/Maintenance phase of the DMAIC process begin. All new nurses and staff will receive the geriatric training. Existing staff will have annual training to review and reinforce their geriatric knowledge. The Lean team will continue to meet monthly, but rapid cycle process improvement will halt unless concerning trends are noted. Sustainability: At 12 and 24 months after Maintenance phase initiation, we will assess the degree of routinization and institutionalization among all 180 ED nurses via a Sustainability survey (estimated response rate 70%).⁵ Implementation support will be withdrawn in a stepwise fashion in 3 month blocks. For example, fidelity audits may be decreased from weekly to monthly to semi-annually. If concerning trends are noted in the monthly aggregate EMR data, these processes will be reinstated and the Lean team will be reconvened. Per STARI guidelines,¹⁰ we will monitor for any contextual changes that occur during this time that may affect results and any adaptations to the protocol. Reporting continued maintenance of a program as the only measure of sustainability is insufficient, as program adaptation may also signal further benefits or sustained improvement.¹¹

III. Aim 2 Protocol

A. Specific Aim: To reduce the decline in functional status and health related quality of life (HRQoL) commonly seen after older adults experience an ED visit.¹²⁻¹⁴ We will recruit cohorts pre and post implementation.

Hypothesis 2a: The intervention will reduce the decline in functional status seen after ED visits. Secondary outcomes include health-related quality of life, ED revisits, and results of the multidisciplinary assessments.

Hypothesis 2b: Patients will be satisfied with the protocol as assessed by thematic analysis of qualitative subject interviews of intervention patients.

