B. Participant Selection: Adults ≥ 65 years assigned to the Obs Unit at the discretion of the treating physician will be enrolled (**n=380**). Patients may be in Obs as part of an Obs protocol (e.g., chest pain) or in response to a positive geriatric screening test. Patients with delirium or dementia will be enrolled with an LAR and patient assent. Exclusion criteria are need for inpatient care, non-English speaking, acute psychiatric issues, prisoners, unable to follow-up, or unable to consent and no LAR.

Study personnel will monitor the Obs Unit electronic tracking board (7am-11pm M-F and select weekends) to identify and recruit 380 patients (150 pre and 230 post cohorts).

C. Data Collection: A survey and chart review will be completed during the Obs stay (Table 3). Follow up phone interviews will occur at days 30 ± 3 and 90 ± 5 . In simulations with research staff, survey completion required 8-10 minutes of patient time. Patient data will be collected in REDCap, which has built in scoring tools for PROMIS measures. Chart abstraction will be done by research coordinators and will use standard methods (including training of abstractors, standardized forms, code book, etc).¹⁵

Data collection definitions:

OARS:¹⁶ (Primary Outcome) An assessment of activities of daily living (functional status) commonly used in ED studies. We will obtain 4 timepoints: Premorbid (patient report of function 1 week prior to ED visit), at the ED visit (day 0), and at days 30 and 90. A change of ≥ 3 points or death between is a significant decline.^{12,17}

HRQoL: The Patient Reported Outcomes Measurement information System (PROMIS) is endorsed by the NIH and PCORI. We will use the Global Health v1.2 (10 questions). A 3 point change is clinically meaningful.¹⁸

New services: Number of new or increased outpatient services (e.g., home health therapies, referral for community interventions, equipment).

New geriatric syndrome¹⁹ diagnoses of delirium, impaired cognition, fall risk, or elder mistreatment.

Geriatric clinic referral: Referrals to the Falls Prevention, Polypharmacy, or Geriatrics Clinic.

Pharmacist recommendations: Number of medication related problems/interactions.^{1,20}

Positive geriatric interventions: ≥ 1 of: new services, diagnoses, referrals, or pharmacist recs.

ED revisits and hospitalizations: Any ED revisits or unscheduled hospitalizations within 90 days.²¹

Patient satisfaction: interview data with themes of positive patient outcomes or satisfaction.

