Table3: Patient level data collected for Aim 2.

	Chart review	Patient interview
Day 0	
 - Demographics and zip code - Charlson Comorbidity Index - Observation protocol - Geriatric screening scores - Geriatric assessments - New geriatric syndromes - Geriatric clinic referrals - Medication recommendations - New services - Disposition and length of stay 	
 - OARS and HRQoL - Current level of care - Falls in the past month - Current home health and community resources - (subset) semi-structured interviews.
Days 30, 90	
 - Clinic referrals and follow-up - ED revisits and 	
 - OARS and HRQoL - Current level of care

	hospitalizations	
 - Falls since last contact - Home health and community resources used
--	------------------	--

Qualitative data: At least 20 patients in the post cohort will be selected for semi-structured interviews. Interviews will be led by a trained researcher coordinator. Purposeful sampling will be used to provide a mix of genders, ages, and Obs Unit dispositions. To assess patient satisfaction, (Aim 2b), a trained researcher will conduct in-person, semi-structured interviews with intervention patients. In addition to Likert-type questions, we will solicit brief descriptions of clinical exemplars of how this intervention produced a positive patient outcome. See interview guide. Maximum variation/heterogeneous purposive sampling will provide a mix of genders, ages, and observation dispositions. This interview will add an additional 20 minutes to the patient's participation time, and so we expect that some participants may decline this portion. With 230 patients in the post implementation cohort, we should have sufficient volume to get at least 20 patients to participate in the qualitative data collection.

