Secondary outcomes for 2a: Dichotomous secondary outcomes will be analyzed using proportions and chi-square tests between pre- and post-intervention groups and with exploratory logistic regression models. Count data will be explored using either Poisson or negative binomial regression. *Exploratory analyses* will use similar methods to compare the pre-intervention group to the post- subgroup who received all 3 screens.

F.12.ii *For Aim 2b,* interviews will be transcribed verbatim and entered into Atlas.ti. We will conduct manifest content analysis of the descriptions using phrases and sentences as our unit of analysis.^{24,25} We will categorize the exemplars and analyze for appropriateness and perceived outcomes based on the level of detail provided. Analysis will include open and axial coding procedures using techniques of constant comparison and questioning within and across cases.^{26,27} The coding schema will be created with consensus on coding definitions and grouping codes into code families/categories. Dual coding with negotiated consensus will be performed on 20% of the data to add rigor to the analysis. Themes will be reported per current guidelines.^{28,29}

V. References

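### The Hypothesis 2b outcome and its only described open-ended prompt name positive experiences only, which tilts the interview findings towards satisfaction

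*Combined protocol and SAP*

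**What the plan says.** Section III.A states Hypothesis 2b as a directional claim: "Patients will be satisfied with the protocol as assessed by thematic analysis of qualitative subject interviews of intervention patients". The definitions in section III.C give the matching outcome: "Patient satisfaction: interview data with themes of positive patient outcomes or satisfaction".

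The Qualitative data paragraph after Table 3 describes the interview as Likert-type questions plus a request for short clinical examples of "how this intervention produced a positive patient outcome". It then refers to a separate document ("See interview guide"), which is not part of the text under review. On numbers it says: "At least 20 patients in the post cohort will be selected for semi-structured interviews". The sample is purposive, and the paragraph expects that some patients will decline the extra 20 minutes.

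The Aim 2b analysis in section IV (F.12.ii) plans verbatim transcription, manifest content analysis of the descriptions, open and axial coding, and constant comparison. Of the exemplars it says: "We will categorize the exemplars and analyze for appropriateness and perceived outcomes based on the level of detail provided". It does not mention the Likert-type items.

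**The concern.** The hypothesis, the prompt and the outcome definition all point the same way. The prompt presupposes that the intervention helped, and the outcome is framed around themes that say it did. If both are followed as written, a report that patients were satisfied would partly reflect what they were asked and what was looked for.

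Also at stake is the patient's own view of burden, such as unwanted assessments or a stay that felt too long. Section II (F.7.ii) has the implementation team look at burden on staff and at adverse effects on ED metrics. The patient interview items in Table 3 cover function, quality of life, level of care, falls and services. Nothing in the text describes asking patients whether the protocol was a burden, so these interviews are the natural place to do it.

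**Working it through.** No test, power or success criterion is stated for Hypothesis 2b, so there is no figure to reproduce. The check is to set the four steps of the plan side by side.

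1. **Claim (III.A).** Patients will be satisfied. Thematic analysis of the interviews is the only assessment named.
2. **Elicitation (III.C, Qualitative data).** Two kinds of content are described: Likert-type questions, whose wording is not given, and a request for examples of benefit. No neutral or negative open-ended prompt is described.
3. **Outcome (III.C, definitions).** Positive outcomes or satisfaction are named. There is no category for neutral, negative or mixed themes.
4. **Analysis (IV, F.12.ii).** Coding is open and not limited to positive codes, but the exemplars to be categorised are those solicited as positive. No negative-case search is planned, and no use of the Likert responses is stated.

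Next, follow three hypothetical patients through these steps.

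- *Satisfied.* The prompt invites the account, the coding captures it, and the outcome definition counts it.
- *Mixed.* The prompt invites the good half. The bad half appears only if it is volunteered or if the guide asks for it. The definition has a place for the good half alone.
- *Dissatisfied.* The patient may have no example to offer, or may volunteer a complaint. Open coding would pick up the complaint. The outcome definition has no place for it, although the absence of positive themes would fail to support satisfaction. A low Likert answer would be recorded, but the analysis section does not say how it bears on 2b.

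Favourable accounts are thus solicited and counted at every step. Unfavourable ones can get in, but only by routes whose content or use the plan does not describe. That asymmetry is the tilt.

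The only arithmetic is descriptive: 20 / 230 = 0.087, or 8.7% of the post cohort. This is a floor, because the plan says at least 20. It shows how small the base is and says nothing about the direction of the tilt. The planned sampling ("Maximum variation/heterogeneous purposive sampling will provide a mix of genders, ages, and observation dispositions") varies patient characteristics but does not seek out unfavourable experience, so it does not offset the prompt.

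**The case against.** The strongest reply is that the plan does not shut out bad experiences.

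- The sentence that asks for positive examples begins by adding them to Likert-type questions, which can record dissatisfaction.
- The interviews are semi-structured and follow a guide that cannot be inspected here. Its prompts may be balanced.
- Open coding, constant comparison and a review of the examples for appropriateness are not confined to favourable codes.
- A definition of satisfaction will naturally mention satisfaction. It does not tell the analysts to discard other themes, and interviews without positive themes would not meet it.

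All of this stands, and it defeats the stronger reading that a reader might infer: that the interviews admit only positive experiences, that they cannot refute Hypothesis 2b, or that the hypothesis is true by construction. The documents do not support any of these.

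Nor do they support the inference that the design conceals longer stays. Length of stay is taken from the chart for each Aim 2 patient (Table 3) and watched as an ED metric (F.7.ii). The interviews also fall in the post cohort, enrolled in months 33-56 (Table 2), when rapid-cycle improvement is due to have halted unless concerning trends appear (F.7.iii). They are therefore not the implementation team's main source of feedback.

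Finally, a small purposive qualitative sample does not need a numeric pass mark. Aim 1 has such rules (a point estimate above 80% for 6 months; mean sustainability subscores below 3.0 reported as weaknesses), but lacking one in 2b is not an error.

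The reply does not remove the tilt. The hypothesis is to be judged by themes, the definition names only favourable ones, and the Likert items are given no part in the conclusion. A balanced guide would repair the elicitation but leave the definition as it is.

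**Conclusion.** The point holds as a tilt, not as a closed loop. The satisfaction outcome and the only open-ended prompt described favour positive accounts, and the plan does not say how contrary evidence would enter the conclusion on 2b. This goes beyond missing detail, because following the stated prompt and definition would itself lean the result towards satisfaction.

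The size cannot be estimated from the documents. The effect is confined to a qualitative sub-aim and does not touch the Aim 2a primary outcome or its chi-square test. The change is still worth making before the interviews, because a question left out then is hard to ask afterwards.

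The conclusion assumes that the analysts apply the section III.C definition as worded. It makes no assumption about the contents of the interview guide. If the guide already has neutral or negative prompts, the elicitation part of the point falls away, while the outcome definition and the unassigned Likert items remain.

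**What to change.** - **III.C, Qualitative data:** replace the prompt, or pair it, with a balanced one that asks how the intervention helped, made no difference, or caused a problem. If the guide already has such a prompt, say so in the protocol.
- **III.C, definitions:** define the 2b outcome over positive, neutral, negative and mixed themes.
- **IV, Aim 2b analysis (F.12.ii):** add a negative-case analysis, and report the Likert satisfaction items alongside the themes when concluding on 2b.

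The cost is one or two more questions in an interview of about 20 minutes, one changed definition, a sentence or two of analysis text and a small amendment to the guide.

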D. Follow up: The participants will be followed for 90±5 days. The follow up interviews will be done over the phone. If the participant prefers, these can be scheduled by email to allow them to choose an appropriate and easy time. Email reminders can also be sent if the participant prefers that communication strategy. LAR or caregivers are invited to be present at during the follow up calls. If the participant and the LAR/caregiver give antithetical answers to a question, both answers will be recorded to track how often this occurs, but only the LAR's answers will be used for the final analysis. All participants will be mailed a Thank you Card from the PI for participating at the end of study enrollment.

IV. Data Analysis

A. Aim 1a outcome definition: **Screening rate** is defined as the percentage of ED patients ≥ 65 years old who have documentation of *all 3 screens* (4SBT, ISAR, Delirium). **Protocol Fidelity** is the percentage of screen positive patients in the Obs Unit who receive *all appropriate consultations* as noted on EMR data. Secondary outcomes include the number of cycles required to reach 80% screening, any protocol adaptations, and fidelity to Lean methods. Fidelity to Lean will be measured by (1) Lean documents, (2) completion of ≥2 rapid improvement cycles, and (3) representation from both leadership and frontline employees at meetings.

Aim 1b outcome definition: We will characterize the necessary elements to maintain screening rates >80%. We will use X-bar and R-charts to evaluate for special process variation as we withdraw implementation support. Any support withdrawal that leads to significant decrease in screening rates will be considered necessary and the Lean team will address the problem. For sustainability, we will summarize and report the mean total and subsection scores at each timepoint. The main outcome is the change in scores over time. Secondly, any mean subscores < 3.0 on the Sustainability Survey will be considered areas of weakness in the protocol and reported as possible threats to sustainability.²²

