Analysis: Monthly summary statistics on geriatric patient visits, screening and consultation will be recorded. For **Hypotheses 1a.i and 1a.ii (Implementation)** we will calculate the proportions for screening rate and protocol fidelity with 95% CIs monthly using aggregate data. Success is predefined as a point estimate >80% for each outcome for 6 months. The Staff Implementation Surveys (both pre- and post-implementation) will be thematically analyzed using Atlas.ti (Cleverbridge, Inc, Chicago, IL) a qualitative data analysis program, and categorized within the CFIR framework. This data will be used to further the implementation process. Additional assessments of implementation will include: the number of improvement cycles, generated solutions and protocol adaptations, and Lean fidelity. Lean fidelity will be assessed as a yes/no variable at conclusion of implementation. For **Hypothesis 1b, (Sustainability)** we will compare the total mean scores (primary outcome) between the 2 years taking into account linked responses by the same nurses in both years using a mixed model. We will compare individuals' scores over time using a paired t-test or Sign Rank test.

B. Aim 2: Participant representativeness will be assessed by comparison to demographics of all ED patients. The *primary outcome* for Aim 2a is the proportion of patients in the pre and post cohort with a significant (≥ 3 point) decline in Functional Status (OARS) from day 0 to day 90. We will compare proportions with decline in the pre- and post-group using a Chi-square test (primary analysis). Also, logistic regression modeling will be used to compare the functional decline between the pre and post intervention groups univariately and while controlling for initial ED HRQoL, demographic factors (age, race, average socioeconomic status from zip code census tract), Charlson Comorbidity Index score,²³ number of services used and any other significant factors varying between the two cohorts. The total number of covariates will not exceed 12, given we estimate 122 subjects with functional decline. A similar secondary analysis will be done using the 30 day timepoint data.

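### Section IV.B restates the primary endpoint for the Aim 2 test without death, although section III.C counts death as a significant decline

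*Combined protocol and SAP*

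**What the plan says.** Section III.C (Data collection definitions) labels OARS the primary outcome and gives the rule: "A change of ≥ 3 points or death between is a significant decline". It lists four assessments: "We will obtain 4 timepoints: Premorbid (patient report of function 1 week prior to ED visit), at the ED visit (day 0"), then days 30 and 90.

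Section IV.B (Data Analysis, Aim 2) compares the proportions of patients in the pre and post cohorts with "a significant (≥ 3 point) decline in Functional Status (OARS) from day 0 to day 90", using a chi-square test as the primary analysis. It adds logistic regression, with covariates capped at 12 on the strength of an estimated 122 declines. On the earlier timepoint it says: "A similar secondary analysis will be done using the 30 day timepoint data". Death appears nowhere in IV.B.

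For days 30 and 90, Table 3 lists under chart review "Clinic referrals and follow-up - ED revisits and" hospitalizations. Under interview it lists OARS and HRQoL, level of care, falls, and services used. No item records whether the patient is alive. Section III.D plans telephone follow-up and says "LAR or caregivers are invited to be present at during the follow up calls".

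**The concern.** The sentence that sets the primary test should carry the endpoint that the plan defines. IV.B does not simply use the defined term and leave the content to III.C. It puts its own criterion in parentheses, and that criterion lacks death.

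A patient who dies before day 90 has no day-90 OARS. An analyst working from IV.B alone could count that patient as declined, leave the patient out, or keep the patient in the denominator as not declined. Only the first agrees with III.C. The other two take the worst outcome out of the event count.

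The cohorts are not randomised and are enrolled in months 3-15 and 33-56, so equal mortality cannot be taken for granted. If the rule stays open, it could be settled after the data are seen.

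**Working it through.** **Inputs from the documents.** Cohorts of 150 (pre) and 230 (post), from III.B; 122 expected declines, from IV.B; chi-square test on two proportions, from IV.B. The documents give no mortality, no cohort-specific decline rates and no significance level.

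**The plan's own figure.** 122/380 = 32.1% overall. It cannot be rebuilt, because the rates behind it are not given, and IV.B does not say whether it includes deaths.

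**Assumptions.** Two-sided 5% level. Decline with deaths counted: 40% pre and 27% post, which gives 150 × 0.40 + 230 × 0.27 = 60 + 62.1 = 122.1 events. This treats the 122 as including deaths. Ninety-day mortality of 2-8%.

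**Patients affected.** 380 × 0.02 = 7.6 and 380 × 0.08 = 30.4, so about 8 to 30.

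**Method.** Let c be the proportion declined with deaths counted and d the mortality in a cohort.

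- Deaths counted (III.C): c, on all patients.
- Deaths excluded: (c − d)/(1 − d), on n(1 − d) patients.
- Deaths coded as not declined: c − d, on all patients.

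P-values are chi-square without continuity correction, on expected counts.

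**Deaths counted.** 40.0% against 27.0%: 13.0 points, p = 0.008.

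**Deaths excluded.** Example at 2% pre and 4% post: (0.40 − 0.02)/0.98 = 38.8%; (0.27 − 0.04)/0.96 = 24.0%; difference 14.8 points.

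| Mortality pre / post | Difference (points) | p |
|---|---|---|
| 2% / 2% | 13.3 | 0.007 |
| 5% / 5% | 13.7 | 0.005 |
| 2% / 4% | 14.8 | 0.0024 |
| 4% / 6% | 15.2 | 0.0018 |
| 5% / 7% | 15.3 | 0.0015 |
| 5% / 8% | 16.2 | 0.0008 |
| 4% / 2% | 12.0 | 0.014 |
| 6% / 4% | 12.2 | 0.012 |
| 7% / 5% | 12.3 | 0.011 |
| 8% / 5% | 11.6 | 0.017 |
| 5% / 2% | 11.3 | 0.021 |

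The extremes are 16.2 − 13.0 = +3.2 and 11.3 − 13.0 = −1.7 points. If the 3-point gap with higher pre mortality is taken only at 8% against 5%, the lower end is 11.6 − 13.0 = −1.4. No row changes the conclusion. With deaths excluded, p first passes 0.05 when pre mortality exceeds post by 5.6, 5.8 or 5.9 points (post mortality 2%, 4% or 5%).

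**Deaths coded as not declined.** The difference is (0.40 − d_pre) − (0.27 − d_post) = 0.13 + (d_post − d_pre), so it moves by exactly the mortality gap: at most 3 points either way for gaps of up to 3 points. At 5% pre and 2% post it is 35.0% against 25.0%, 10.0 points, p = 0.036.

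**A borderline result, in whole patients.** Take 3 pre and 9 post deaths (2.0% and 3.9%) and 122 events in all.

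- 55/150 against 67/230: p = 0.124. Deaths excluded, 52/147 against 58/221: p = 0.061.
- 56/150 against 66/230: p = 0.078. Deaths excluded, 53/147 against 57/221: p = 0.035.

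In both, exclusion lowers p. Whether it crosses 0.05 turns on one event moving between cohorts.

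**The case against.** The best defence is that III.C defines the term and IV.B uses it, so the parenthesis in IV.B is shorthand and deaths carry over. That is probably the intent. It does not remove the conflict, because the parenthesis restates the criterion and restates it differently.

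Three stronger readings are tempting, and the documents support none of them.

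- *That IV.B makes the analysis survivor-only.* A reader might infer this from the missing day-90 OARS. But IV.B speaks of the proportion of patients in each cohort and never restricts the denominator. Exclusion is no more stated than coding deaths as not declined.
- *That the window for death is undefined.* The III.C sentence names no interval, but IV.B supplies day 0 to day 90 for the primary test, and a similar analysis at day 30 naturally runs from day 0 to day 30.
- *That deaths would be recorded as loss to follow-up.* Table 3 is a summary list, not the case report form, and a missing row does not show this. The calls, which caregivers may join, and the chart review would reveal many deaths.

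It is also fair to say that every mortality and decline rate used here is assumed, that mortality may be low because "Exclusion criteria are need for inpatient care", and that the borderline example depends on a single patient. All of that stands. It limits the size of the point, not the mismatch.

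**Conclusion.** The point holds as an internal inconsistency in the primary endpoint: IV.B is wrong as written, because its criterion differs from the III.C definition it should apply. The text comparison needs no assumption.

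The expected effect is modest. In the illustration, excluding deaths shifts a 13.0-point difference by about −1.7 to +3.2 points for mortality gaps of up to 3 points, without changing the conclusion. This rests on assumed mortality of 2-8%, assumed decline of 40% and 27%, and the assumption that the planned 122 events include deaths. A large mortality gap or a result near the significance threshold could be sensitive. The documents give no reason to expect either, so it would go too far to say that the primary conclusion is at risk.

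**What to change.** In IV.B, state the endpoint in full: OARS at day 90 at least 3 points worse than at day 0, or death by day 90, with patients who die counted in both numerator and denominator. Use the same form for the day-30 analysis, with day 30 in place of day 90. Add a vital-status field at days 30 and 90, filled from the calls and chart review already planned, so that a death can be told apart from a patient who was not reached.

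The cost is one sentence in IV.B and one data field, with no new contacts. The small downside is that the composite is slightly less specific to function, but that is already so under III.C.

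### The primary Aim 2a test is an unadjusted chi-square between non-randomised before/after cohorts; the adjusted model is only an addition, omits baseline OARS by name and leaves its covariates partly open

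*Combined protocol and SAP*

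**What the plan says.** Section IV.B defines the primary Aim 2a outcome as the proportion of patients in each cohort whose OARS falls by 3 points or more between day 0 and day 90. On the test it says: "We will compare proportions with decline in the pre- and post-group using a Chi-square test (primary analysis"). It then adds logistic regression of functional decline on cohort, univariately and adjusted. The named covariates are initial ED HRQoL, age, race, area socioeconomic status and Charlson score, followed by "number of services used and any other significant factors varying between the two cohorts". The total is capped at 12 covariates because 122 patients are expected to decline.

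Section III.B sets the same entry criteria for both cohorts (150 before, 230 after), with placement decided by the treating physician. It also states: "Patients may be in Obs as part of an Obs protocol (e.g., chest pain) or in response to a positive geriatric screening test". Section I.B gives current screening as 5% of older ED patients and the target as above 80%.

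Section III.C collects OARS four times, including "Premorbid (patient report of function 1 week prior to ED visit), at the ED visit (day 0"). It lists new services as a measure in their own right: "Number of new or increased outpatient services". In Table 3 the day-0 interview records "Current level of care - Falls in the past month - Current home health and community resources", while the day-30 and day-90 interviews record "Home health and community resources used".

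**The concern.** The treatment contrast is calendar period, and the programme can alter who is in the Obs Unit in the later period. If more patients enter because of a positive screen, and their risk of decline differs from that of patients on, say, a chest pain protocol, the crude difference mixes that shift with any effect of the protocol. The chi-square cannot separate the two. Listing covariates shows that the plan expects the cohorts may differ, yet the result it designates as primary takes no account of this.

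The adjusted model has three gaps of its own.

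- **Baseline OARS is not named.** It could enter only through the clause on significant differences between cohorts, for which no threshold is given. Using day-0 OARS to form the change does not control for it: a patient near the bottom of the scale has little room to lose 3 points.
- **Covariates are partly chosen from the data.** The final model is therefore not known in advance.
- **Services used has no time point.** It can be read as the day-0 item or the follow-up item. Services received after the Obs stay may be part of how the protocol works, so adjusting for them could remove some of the effect under test.

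**Working it through.** **1. The plan's own figure.** 150 + 230 = 380, and 122/380 = 32.1% pooled decline. 122/12 = 10.2 events per covariate, so the cap of 12 is consistent with the expected events. The split of the 122 between cohorts is not given, and the figure cannot be rebuilt from stated rates.

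**2. What the documents give about bias.** They give neither the share of Obs patients who are screen-placed nor the decline risk by route of entry. The 11% in Section I.B is a different quantity (older adults placed in the Obs Unit for further assessment). Size and direction therefore cannot be computed, and what follows is illustration.

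**3. Illustration, inputs assumed.** No protocol effect; 122 events in total; screen-placed share g of 11% before and 30% after; screen-placed patients at RR times the risk of other Obs patients; two-sided 5% test.

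Cohort risk = r × (1 − g + g × RR), with r solved so that 150·p1 + 230·p2 = 122. For RR = 2 the multipliers are 1.11 and 1.30, so r = 122/(150 × 1.11 + 230 × 1.30) = 122/465.5 = 0.2621, p1 = 29.1% and p2 = 34.1%. The pooled SE is √(0.321 × 0.679 × (1/150 + 1/230)) = 0.0490 and the unpooled SE is 0.0485. The chance of a false finding of harm is Φ((0.0498 − 1.96 × 0.0490)/0.0485) = 17.0%. The same steps give:

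| Share before → after | RR | Before | After | Shift (points) | False benefit | False harm | Two-sided |
|---|---|---|---|---|---|---|---|
| 11% → 30% | 0.5 | 34.2% | 30.7% | −3.4 | 10.5% | 0.4% | 10.9% |
| 11% → 30% | 1 | 32.1% | 32.1% | 0 | 2.5% | 2.5% | 5.0% |
| 11% → 30% | 1.5 | 30.5% | 33.2% | +2.7 | 0.6% | 8.0% | 8.5% |
| 11% → 30% | 2 | 29.1% | 34.1% | +5.0 | 0.1% | 17.0% | 17.2% |
| 11% → 20% | 0.5 | 33.1% | 31.5% | −1.6 | 5.1% | 1.1% | 6.2% |
| 11% → 20% | 2 | 30.6% | 33.1% | +2.5 | 0.7% | 7.2% | 7.9% |
| 11% → 11% | any | 32.1% | 32.1% | 0 | 2.5% | 2.5% | 5.0% |

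A simulation of the uncorrected chi-square (400,000 runs) agrees: false benefit 10.7% at RR 0.5 and false harm 16.9% at RR 2, both for 11% → 30%. For scale, the 95% CI half-width of the crude difference is 1.96 × 0.0490 = 9.6 points.

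**4. Services used, follow-up reading, extreme case.** Assume services reach 20% before and 70% after, decline risk is 19.2% with services and 45.2% without, and services carry the whole effect. Then decline is 0.2 × 19.2% + 0.8 × 45.2% = 40% before and 0.7 × 19.2% + 0.3 × 45.2% = 27% after. In 3,000 simulated trials, adjusting for services cut power from 75% to 5%. With only part of the effect carried by services, the loss would be smaller.

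**5. Room in the model.** Premorbid OARS, HRQoL, age, race, area SES, Charlson and day-0 services are 7 covariates; falls and level of care make 9; the cohort term makes 10 parameters if each takes one: 122/10 = 12.2. With race at 3 df (assumed) there are 12: 122/12 = 10.2. If level of care has three categories (assumed), there are 13: 122/13 = 9.4. Adding day-0 OARS to the 10-parameter model gives 122/11 = 11.1; adding it to the 12-parameter model gives 122/13 = 9.4.

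**The case against.** The strongest reply is that the adjusted analysis is already planned, with sensible covariates and a cap, so both results will be available and the request is largely about labels. That is true, and it makes the change cheap. But if the two disagree, the plan as written makes the crude p-value the result, and the model's contents are still not fixed.

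A second reply is that the shift may be small. This stands. Entry criteria do not change, placement stays with the physician and follows standard care (Sections I.B and III.B), and the intervention has run since 2015, so the earlier cohort can also include screen-placed patients. The illustration shows that bias is possible, not that it will occur.

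A third is that adjustment is not shown to cure the modelled problem. This also stands: route of entry is not among the proposed covariates, and no error rate after the fix has been derived for this covariate set.

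A reader might infer more than the text allows:

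- **That the crude test favours the programme.** The documents support neither direction. Lower-risk screen-placed patients would mimic benefit; higher-risk ones would mask it or look like harm.
- **That rejection is at least 10.9% throughout.** The 10.9% and 17.2% belong to the two extreme risk ratios; between them it falls to 5%.
- **That the day-90 adjusted model is formally labelled secondary.** Section IV.B uses that word only for the day-30 analysis. The lower standing follows from the chi-square alone being called primary.
- **That services used means follow-up use.** The wording resembles the follow-up item, but the covariates listed with it are day-0 items, so the baseline reading is just as natural.

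**Conclusion.** The point holds on the text. An unadjusted test is primary for cohorts whose case mix the programme can change. The adjusted model is only an addition, does not name baseline OARS, uses an undefined significance screen and leaves the timing of services open. The size and direction of bias are unknown. Under the assumptions in step 3, two-sided rejection with no true effect runs from 5% to 17.2% if the screen-placed share rises to 30%, from 5% to 7.9% if it rises to 20%, and stays at 5% if it does not change. This should be fixed before the before/after comparison is analysed. Confidence is medium: the wording defect is certain, its consequence is not.

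**What to change.** In Section IV.B:

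1. Make the planned covariate-adjusted logistic comparison the primary analysis, reported as a standardised risk difference with 95% CI. Keep the chi-square as supporting.
2. Pre-specify premorbid OARS, initial ED HRQoL, age, race, area SES, Charlson score and services in use at day 0 (the day-0 item in Table 3).
3. Replace the significance screen with pre-named collected baseline factors, for example falls in the past month and current level of care.
4. Report a sensitivity model that adds day-0 OARS, noting that it also defines the change outcome. Putting premorbid rather than day-0 OARS in the primary model is a judgement, and the SAP should state it.
5. Count every parameter, including the cohort term and all levels of race and level of care, against the 122 expected events, and collapse levels if needed.
6. Tabulate each cohort by the Table 3 items "Observation protocol - Geriatric screening scores".

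The cost is SAP wording; every item named is already collected. The downside is that the primary result becomes model-based. Adjustment reduces measured case-mix differences only. It is not shown to remove selection by route of entry, and it does not address time trends between the enrolment windows (months 3-15 and 33-56, Table 2). With screening at 5% before implementation, screening results may be missing for many patients in the earlier cohort, so that part of the tabulation will be less complete.
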